Vendor/Collaborator	Adelphi Real World Ltd	
Rationale	This study will provide data on patient characteristics and treatment patterns of HIV positive patients initiating raltegravir 1200mg once daily (RAL OD) (2 x 600mg). There is a lack of published real world data on the use of once daily raltegravir, and these data will show how RAL OD is used in the real world setting in the UK.	
Primary Objective	To describe and understand the real world utilisation of RAL OD.	
Primary Outcome measures	Description of patient demographics (age, gender, and ethnicity), baseline clinical and treatment characteristics (co-morbidities, co-medications, AIDS defining illnesses within the last 6 months/ever) in ART naïve and experienced HIV-1 infected adult subjects. Description of Antiretroviral therapy (ART) treatment combination initiated with RAL OD. If treatment experienced, description of prior ART regimen. Description of clinical and treatment characteristics (co-morbidities, co-medications) of subjects who remain on RAL OD at the 6 month time point. Description of any change in clinical and treatment characteristics from baseline to 6 months in subjects who	
Secondary Data Collection Objective	remain on treatment Laboratory parameters at baseline and 6 months (HIV viral load, CD4 cell count), RAL OD discontinuations at 6 months	
Study Design	Non-interventional, observational, multi-centre, retrospective chart review study	
Study Population	HIV-1 infected adults initiating RAL OD as part of their ART at treatment centres within the UK from September 2017	
Study Duration	The study duration is expected to be 6-12 months. Patient data will be collected on all patients starting RAL OD from September 2017 who return for their 6 month (-1/+3 months window) follow up appointment. Eligible patients	

Protocol/Amendment No.: RETRO STUDY, v0.3

VEAP ID NO: 7651

	must have completed their 6 month follow up before 31st		
	December 2018		
Exposure and Outcome	Exposure: RAL OD based ART		
	Outcomes: descriptive utilisation and treatment patterns.		
	Clinical measures (HIV viral load and CD4 cell counts)		
	will be captured as secondary endpoints.		
Statistical Methods	The profile of HIV-1 positive subjects initiating treatment		
	with RAL OD will be analysed descriptively using		
	summary statistics.		
Sample Size and Power	Sample size of 300 across 2 centres. This is large enough		
Calculations	to provide precise estimates overall and allow sub-group		

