	assessments. This will be a descriptive analysis - power		
	calculations are therefore not applicable.		
Limitations	Retrospective Database Analysis carries the potential for		
	missing data.		
	Non-randomised: Sampling limited to sequential		
	systematic sampling due to treatment being newly		
	available		

1 **Background and Rationale**

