3 METHODOLOGY

3.1 Summary of Study Design

This is a non-interventional, retrospective observational chart review study at 2 UK treatment centres that will utilize electronic data capture (EDC) to address study objectives.

The study will capture data from 300 HIV-1 positive adult subjects receiving RAL OD as part of their ART at UK NHS treatment centres. NHS records generally capture all of the usual care of an HIV positive patient including their physical exams, diagnoses, laboratory findings, medication prescriptions, co-morbidities, social history and demographic data.

All eligible HIV-1 infected adult patients (\geq 18 years) who initiated RAL OD based ART from September 2017 will be included in this study on a sequential sampling basis. Data from eligible patients' medical charts will be extracted for the time of initiation and at 6 months (window of -1/+3 months) post-initiation follow up appointment.

The index ARV regimen is defined as the first RAL 1200mg OD (2 x 600mg) containing ARV regimen a patient receives and the baseline will be defined as the RAL 1200mg OD

Protocol/Amendment No.: RETRO STUDY, v0.3

VEAP ID NO: 7651

initiation prescription date. Treatment with RAL OD must have been initiated during or after September 2017 and before April 1st 2018 for the primary baseline data collection. Subjects should have at least one 6 month (-1/+3 months) follow up appointment before December 31st 2018 to ensure 6 month secondary outcomes data are available for analysis. Chart review will only be carried out once a patient has completed the 6 month visit to ensure all data are captured retrospectively.

This time period was selected based on expectations of RAL OD utilization over time in the post-launch period and standard UK practice of 6-monthly clinic appointments.

The final analysis will be conducted following database lock after the last study participant has reached the 6 (-1/+3) months treatment milestone, by December 31st^h 2018, and all data queries have been resolved.

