3.2 Study Population

The study will be conducted in 2 NHS hospital HIV departments in the UK. To ensure the data are representative of the UK, centres will be chosen to represent London and non-London in proportion with the treated patient population. As approximately 50% of UK HIV patients are treated in London, one of the potential sites will be selected from the largest treatment centres in London. The additional site will be a non-London treatment centre, and will be selected primarily based on the number of eligible patients treated.

Patients who were initiated on RAL OD at least 6 months ago will be identified by the clinician, Principal Investigator or a member of the clinical team, from review of hospital records and databases as appropriate at each centre. From a list of eligible patients with the required data, the earliest recent record will be recorded as the first participant and then all further eligible participants up to 150 per centre will be selected sequentially to minimize bias.

It is intended that approximately 150 patients will be included from each participating centre to represent a proportionate spread. Oversampling may be performed in the larger centre in order to maintain an overall sample size of 300.

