8.2.1 Methods to Minimize Bias

By including 2 treatment centres we hope to reduce single centre bias. Furthermore, to minimise bias and to ensure a sample population which is representative of UK, site selection will be based on treatment hubs within areas of high prevalence.

As approximately 50% of UK HIV patients are treated in London one of these treatment centres will be randomly selected from the 6 largest treatment centres in London. The other treatment centre will be a non-London centre.

Patients who from September 2017 were initiated on RAL OD for at least 6 months and who completed their 6 month follow up before 31st December 2018, up to 150 patients per site initially, will be selected sequentially to minimise bias. Should the larger site continue to recruit additional patients in order to meet the target of 300, the same methods will be used.

Protocol/Amendment No.: RETRO STUDY, v0.3

VEAP ID NO: 7651

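### Inclusion of all eligible starters conflicts with sequential selection to a limit; if the order is by start date, a centre above its limit loses its latest starters

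*Protocol*

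**What the plan says.** Two statements describe a census. The synopsis, under Study Duration, says "Patient data will be collected on all patients" who start RAL OD from September 2017 and return at 6 months. Section 3.1 says that eligible adults "who initiated RAL OD based ART from September 2017 will be included in this study on a sequential sampling basis". The same section also sets the total at 300.

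Two statements describe a quota. In section 3.2, from a list of eligible patients, "the earliest recent record will be recorded as the first participant". For the patients after that one, the rule in the same section is that "all further eligible participants up to 150 per centre will be selected sequentially to minimize bias". Section 8.2.1 repeats the rule as "up to 150 patients per site initially, will be selected sequentially to minimise bias".

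The per-centre figure is not a hard ceiling. Section 3.2 adds: "Oversampling may be performed in the larger centre in order to maintain an overall sample size of 300". Section 8.2.1 adds: "Should the larger site continue to recruit additional patients in order to meet the target of 300, the same methods will be used".

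The synopsis lists the sampling method as a limitation ("Non-randomised: Sampling limited to sequential" systematic sampling) and gives as the reason that the treatment is newly available.

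**The concern.** A census and a quota agree only while each centre's eligible patients fit within its limit. Beyond that point someone is left out, and the order of selection decides who. If the order runs forward from the first start date, those left out are the most recent starters.

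This bears on the primary objective, which is to describe how and to whom RAL OD is prescribed in the UK. Section 3.1 says the period was chosen on expected use over time after launch. A sample that stops part-way through describes the launch phase and is silent on what follows. Sections 3.2 and 8.2.1 present the sequential order as a protection against bias. It does protect against hand-picking of charts, but not against a shift in prescribing over calendar time.

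Novelty of the drug would explain sequential accrual in a prospective study. Here the initiation window was already closed: the AIDS case-definition entry in the reference list carries an access date of 5/5/2018, after both window ends given in sections 3.1 and 3.3. Every starter could by then be listed.

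**Working it through.** **The plan's own figure.** 2 centres × 150 = 300, which reproduces the stated total.

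**Inputs from the protocol.** Initial limit 150 per centre; total 300; start of window September 2017. The end of the window is given as before 1 April 2018 in section 3.1 (212 days from 1 September 2017) and before 30 April 2018 in section 3.3 (241 days).

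**Inputs that are assumptions.** The protocol gives no eligible number per centre. Let M be the number eligible at the larger centre and s the number supplied by the other centre. M is varied from 150 to 300 and s from 50 to 150. Selection is taken to run by start date.

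**Limit at the larger centre.** L = max(150, 300 − s). So s = 150 gives 150, s = 120 gives 180, s = 100 gives 200 and s = 50 gives 250.

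**Number omitted.** M − min(M, L), shown with its share of M:

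| M | s = 150 (L = 150) | s = 120 (L = 180) | s = 100 (L = 200) | s = 50 (L = 250) |
|---|---|---|---|---|
| 150 | 0 | 0 | 0 | 0 |
| 200 | 50 (25%) | 20 (10%) | 0 | 0 |
| 250 | 100 (40%) | 70 (28%) | 50 (20%) | 0 |
| 300 | 150 (50%) | 120 (40%) | 100 (33.3%) | 50 (16.7%) |

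These shares do not depend on how uptake is spread over the window. Only the calendar date of the cut-off does.

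**Cut-off date, even uptake, L = 150.** 1 September 2017 + D × 150/M days, where D is the window length:

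| M | D = 212 | D = 241 |
|---|---|---|
| 200 | 7 Feb 2018 | 28 Feb 2018 |
| 250 | 6 Jan 2018 | 23 Jan 2018 |
| 300 | 16 Dec 2017 | 30 Dec 2017 |

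**Sensitivity to uptake shape.** On a 7-month window, even uptake puts the cut-off at month 7 × 150/M = 5.3, 4.2 or 3.5 for M = 200, 250 or 300. Linearly rising uptake puts it at month 7 × √(150/M) = 6.1, 5.4 or 4.9.

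**Effect on an estimate.** Let f be the omitted share, and p_early and p_late the proportions with some characteristic among those sampled and those omitted. The centre's true proportion is (1 − f) p_early + f p_late, and the sample estimates p_early, so the bias is f × (p_early − p_late). At f = 25%, 40% or 50% this is a quarter, two fifths or half of the early-to-late difference. The protocol gives no figure for that difference, and a larger quota reduces the bias only by reducing f.

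**The case against.** The strongest reply is that this is ordinary consecutive enrolment to a target. The sentence in section 3.1 itself ends with a reference to sequential sampling, section 8.2 speaks of consecutive patients, and the synopsis discloses the limitation. Section 8.3 frames the aim as initial utilisation, and nothing shows that either centre has more than 150 eligible. This stands in part. The effect is conditional, and it is nil within the limit. It does not rescue the wording: the synopsis still promises all patients, and a launch-weighted sample is not what the window in section 3.1 was chosen to capture.

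A second reply concerns timing. Starters are known early, but eligibility requires a 6-month visit completed before 31 December 2018, and a conference submission is planned for mid January 2019. A draw from the finished list of eligible patients would come too late. That is correct, but it is met by randomising the order of the starters, who are known once the window closes, rather than drawing from the final eligible list.

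A reader might also infer four stronger things that the protocol does not support:

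- *Later starters at a large centre can never be selected.* Sections 3.2 and 8.2.1 let the larger centre pass 150 when the other falls short. With 200 eligible there and 100 supplied by the other centre, nobody is omitted.
- *The sponsor expects the larger centre to exceed 150.* The oversampling clause is permissive and reads as a contingency for a shortfall; section 8.3 says sample size depends on uptake.
- *Extending the larger centre confounds centre with calendar time.* A centre that falls short has used its whole list and so spans the whole window. Extending the other moves its coverage towards that same span. No comparison between centres is planned.
- *Order by start date is stated.* The text names a record, not a start date. Start-date order is an inference from the words sequential and consecutive.

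**Conclusion.** The point holds in a conditional form. The census wording in the synopsis and section 3.1 cannot be followed together with the quota in sections 3.2 and 8.2.1 once a centre's eligible number exceeds its limit. If selection follows start date, the patients dropped are then the latest starters, so the claim that the method minimises bias is not justified for describing prescribing across the window.

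The size rests on assumed centre totals. At a limit of 150, a centre with 200, 250 or 300 eligible omits its last 25%, 40% or 50%. With 120 from the other centre, a centre with 200 eligible omits 10%. Within the limit the omission is zero. Whether early and late starters differ, for example in the share switching from RAL BID, is plausible but not documented. The correction is worth making because it costs little and has no effect on who is sampled if the limit is never reached.

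**What to change.** State one selection rule, in the same words, in the synopsis and sections 3.1, 3.2, 8.2 and 8.2.1:

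1. Each centre lists every patient who started RAL OD in the initiation window. The two end dates in sections 3.1 and 3.3 must first be reconciled.
2. The list is put in random order once, before chart review.
3. Charts are reviewed in that order as 6-month visits complete. A patient whose visit is pending keeps their place and is not passed over for someone lower on the list; otherwise early starters would be favoured again.
4. If the eligible patients are within the limit, all are taken; otherwise selection stops at the limit.
5. Any top-up at the larger centre continues down the same random list.
6. The report gives numbers listed, eligible and sampled by centre and start month.

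Replace the census wording and the reference to the earliest record accordingly, and remove the synopsis statement that novelty of the drug restricts sampling to sequential.

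The cost is wording and one random ordering of a list that the centres can compile from their records. The number of charts is unchanged, and hand-picking is still prevented. The downsides are loss of strict consecutiveness and slightly later availability of some charts.

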3.3 Inclusion Criteria

HIV-1 infected patients initiating RAL OD based ART during or after September 2017 and before April 30th 2018 will be included in the study sample if they meet the following inclusion criteria:

- 1) A diagnosis of HIV-1 infection
- 2) At least 18 years of age at the index date

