8.2 Bias

It is intended that data will be collected on consecutive patients in who at least 6 months follow-up was possible (i.e. started RAL OD during or after September 2017). Eligible patients must have completed their 6 month follow up before 31st December 2018. This will include any patients who may have moved treatment centres since initiation. Participating centres will be selected to be representative of the UK population, one site from within London (where approximately 50% of HIV patients in the UK are currently treated) and one from outside London will be used.

The study is a retrospective chart review study that will be using data extracted from databases; any missing data will be queried with the sites and if not available, will be recorded as such.

Any observational study has the possibility of residual confounding due to unknown risk factors [13]. However this study is designed to collect information on recent prescribing practice and is based on clinical experience and knowledge of the HIV physician.

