8.3 Sample Size and Power Calculations

Sample size will depend on the uptake and capture of RAL OD data in the selected sites. The uptake of RAL OD in these sites is expected to be sufficient to assess the primary objective of characterising the initial utilisation of RAL OD in 300 subjects, provide precise estimates overall, and allow sub-group assessments.

As this is a descriptive study no power calculations will be carried out.

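### Sections 3.1 and 3.3 give different last initiation dates (before 1 April and before 30 April 2018), and only the earlier one fits the follow-up window and the 31 December 2018 limit

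*Protocol*

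**What the plan says.** Two current sections of the protocol set the end of the initiation period.

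- Section 3.1 (Summary of Study Design): treatment must have been "initiated during or after September 2017 and before April 1st 2018 for the primary baseline data collection".
- Section 3.3 (Inclusion Criteria): the study sample consists of HIV-1 infected patients "initiating RAL OD based ART during or after September 2017 and before April 30th 2018".

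The limit on follow-up is the same wherever it appears. Section 3.1 states: "Subjects should have at least one 6 month (-1/+3 months) follow up appointment before December 31st 2018". Section 8.2 makes it a condition of eligibility: "Eligible patients must have completed their 6 month follow up before 31st December 2018". The synopsis and section 8.2.1 carry the same limit. Section 3.1 also places the final analysis after database lock, "after the last study participant has reached the 6 (-1/+3) months treatment milestone, by December 31st" 2018.

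The synopsis and sections 8.2 and 8.2.1 give a start of September 2017 but no end of initiation, so they do not settle which date applies. Sections 3.2 and 8.2.1 describe sampling in sequence from the earliest record, up to 150 patients per centre, with more from the larger centre if needed to reach 300.

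**The concern.** A patient who started RAL OD between 1 and 29 April 2018 is in the study under section 3.3 and out of it under section 3.1. Each centre's own clinical team draws up its list of eligible patients (section 3.2), so one site could stop at the end of March and the other at the end of April, both following the protocol. Section 8.1.2 defines the primary population, and the denominator for the secondary objective, as all who initiated RAL OD. The cut-off therefore helps to decide who stands in every reported proportion.

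The later date also sits badly with the follow-up limit. Completed follow-up is a condition of entry, and charts are reviewed only after the 6-month visit. An April starter whose only in-window visit falls after the limit is left out, while an earlier starter seen the same length of time after initiation is kept. Because section 8 allows no imputation and uses observed data only, such a patient simply does not appear.

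**Working it through.** No alpha, power or effect size enters here (section 8.3: "As this is a descriptive study no power calculations will be carried out"). The check is calendar arithmetic.

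**Inputs**

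- Last eligible start: 31 March 2018 (section 3.1) or 29 April 2018 (section 3.3).
- Visit window: 6 months, -1/+3 months, that is from month 5 to month 9 after initiation (synopsis, sections 2.2 and 3.1).
- Follow-up limit: before 31 December 2018 (synopsis, sections 3.1, 8.2 and 8.2.1). Read strictly, the last allowed day is 30 December.

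**Step 1. Reproduce the protocol's limit.** Window close = start + 9 months. For the last start under section 3.1, 31 March 2018 + 9 months = 31 December 2018. This is the stated limit, or one day past the last allowed day on the strict reading.

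**Step 2. Apply the same rule to the April starts.** Days lost = window close minus 30 December 2018.

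| Start | Month 5 | Month 6 | Month 9 (window close) | Days lost, strict reading |
|---|---|---|---|---|
| 30 Mar 2018 | 30 Aug | 30 Sep | 30 Dec 2018 | 0 |
| 31 Mar 2018 | 31 Aug | 30 Sep | 31 Dec 2018 | 1 |
| 1 Apr 2018 | 1 Sep | 1 Oct | 1 Jan 2019 | 2 |
| 29 Apr 2018 | 29 Sep | 29 Oct | 29 Jan 2019 | 30 |

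A start on day k of April closes on day k of January 2019 and loses k + 1 days. The mean over 1 to 29 April is (2 + 30)/2 = 16 days.

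**Step 3. What remains for the last April starter.** For a start on 29 April the full window is 122 days, of which 122 - 30 = 92 remain. Of the 92 days after month 6, 92 - 30 = 62 remain, so the tolerance falls from +3 to about +2 months. The month-6 date, 29 October 2018, is well inside the limit.

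**Step 4. An illustration.** Take a single in-window visit 8 months and 15 days after initiation. From 31 March it falls on 15 December 2018 and qualifies. From 29 April it falls on 13 January 2019 and does not, although it lies inside the window.

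**Step 5. Size of the disputed period.** From 1 September 2017 to 31 March 2018 is 212 days; to 29 April 2018 it is 241 days. The difference is 29 days, and 29/241 = 12.0%. This is a share of calendar days, not of patients.

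**The case against.** The strongest defence is that section 3.1 ties its date to the primary baseline data collection, so the two dates might serve different purposes. That does not hold: section 3.3 defines the whole study sample, and no section gives April starters a separate role.

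The other objections have more force.

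- **The window is a tolerance.** The protocol does not promise every patient the full +3 months, and section 3.1 cites 6-monthly appointments as standard UK practice. The expected visit of every April starter falls before the limit. This stands. A reader might infer that April starters get in only if they attend early, or that all of them have about +2 months. Neither follows: the loss runs from 2 to 30 days, and early, on-time and moderately late visits all qualify.
- **Sampling is earliest-first to a quota.** April starters are last in line. If the centres fill their quotas from earlier starters, nobody is affected. This also stands, so 12% should not be read as the affected share of the sample.
- **Distortion of results is not shown.** A reader might infer that retention or missingness is biased by calendar time. The documents support this only as a possibility. The study is descriptive, no analysis by calendar time is stated, selection on a completed visit applies to every patient, and neither the direction nor the size of any extra effect can be derived.
- **The earlier date is not an exact fit either.** On a strict reading of the limit, a 31 March starter is one day short. This is correct, and the fix should cover it.

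None of these objections removes the contradiction over who is eligible.

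**Conclusion.** The eligibility period is contradictory as written, and the conflict should be settled before the sites build their patient lists. Starts on 29 calendar days, 1 to 29 April 2018, are eligible under section 3.3 and ineligible under section 3.1. The 1 April cut-off is the one consistent with the visit window, the follow-up limit and the lock date, apart from the one day noted above.

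The consequence of keeping the later date is limited to late attenders among April starters. How many patients that is cannot be worked out, because the protocol gives no monthly uptake. It is zero if the quotas fill before April. If uptake is uniform and all initiators are sampled, about 12% of the sample would be April starters, and only the late attenders among them would be lost. The days-lost figures assume calendar-month arithmetic and a strict reading of the limit; if 31 December itself is allowed, each is one day smaller.

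**What to change.** Use one initiation cut-off in sections 3.1 and 3.3: before 1 April 2018. Word the follow-up limit as on or before 31 December 2018 wherever it appears (synopsis, sections 3.1, 8.2 and 8.2.1), so that a 31 March starter has the full window.

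This changes one date and one phrase. The price is that April starters are no longer available towards the target of 300, which matters only if uptake up to the end of March is too low to fill it.

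If the sponsor wants April starters with a full window, the follow-up limit and the lock date would have to move to about the end of January 2019 throughout. That conflicts with the mid-January 2019 abstract submission in section 10, and it is not needed to resolve the contradiction.
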